## 5. SAMPLE SIZE CONSIDERATIONS

For Part A, Part B, Part E, and Part G, the choice of the number of subjects is based on the classical 3 + 3 design. The approximate sample size in the dose escalation cohorts in Part A will be 36 evaluable subjects assuming that 6 subjects are assigned at each of 6 planned dose levels. The approximate sample size of the dose escalation cohorts in Part B will be 24 evaluable subjects assuming that 6 subjects are assigned at each of 4 planned dose levels. The approximate sample size of the dose escalation cohorts in Part E will be 18 evaluable subjects assuming that 6 subjects are assigned at each of 3 planned dose levels. The approximate sample size of the dose escalation cohorts in Part G will be 12 evaluable subjects assuming that 6 subjects are assigned at each of 2 planned dose levels.

Approximately 8 additional subjects will be enrolled in safety/PK/Pharmacodynamics expansion cohorts at each of 2 or more dose levels in Parts A (AP1, AP2) and B (BP1, BP2) to obtain additional safety and PK/Pharmacodynamics data. Subjects may also be added if exploration of intermediate dose level(s) of JTX2011 is warranted or if the SMC recommends adding additional subjects at a given dose level to further understand and clarify safety issues.

Approximately 120 subjects may be enrolled in Part C (approximately 15 in each cohort). Approximately 90 subjects may be enrolled in Part D (approximately 15 subjects per cohort). For Parts C and D, a group sequential design will be used to evaluate the preliminary efficacy of JTX-2011 or JTX-2011 in combination with nivolumab, with an interim look for futility. A 90% power at a 2-sided  $\alpha$  will be achieved for the hypothesis testing by enrolling 15 subjects (no more than 2% of  $\beta$  spent at interim) as the first step, and a potential expansion up to approximately 49 subjects per cohort if the futility boundary is passed based on the result from the first 15 subjects for each cohort. Using the same alpha and a non-binding futility analysis at 40% of evaluable subjects (17) with a Gamma spending function of -3 provides 80% power to rule out 13% in favor of 28%.

## 6. ANALYSIS POPULATIONS

### 6.1 SAFETY ANALYSIS SET

The Safety Analysis Set (SAF) will be defined as those subjects who receive any portion of study drug (JTX-2011 and/or nivolumab and/or ipilimumab and/or pembrolizumab) where indicated. Subjects will include dose escalation and dose expansion portions of this clinical trial. Subjects will be identified as receiving study drug if the dose start date is completed on the electronic Case Report Form (eCRF). Subjects will be categorized to the planned dose group and actual dose received where actual is considered the initial/first dose received.

#### 6.1.1 SUBSETS OF THE SAF

- Response Evaluable Set: subjects in SAF who have a baseline tumor assessment, and either has at least one post-baseline tumor assessment scan and/or discontinued treatment due to death or disease progression.
- The DLT Evaluable Set: SAF subjects in Phase 1 parts (A, B, E, G) who receive at least one dose of JTX-2011 during the DLT-evaluation period (1st cycle) and complete the DLT-evaluation period (1st cycle) or experience any DLTs.
- Biomarker Analysis Set: SAF who have a baseline sample and at least one post treatment biomarker sample.
- ADA Analysis Set: SAF who have a baseline sample and at least one post treatment ADA sample.

## 6.2 PHARMACOKINETIC ANALYSIS SET

The PK analysis Set will consist of all subjects with at least one quantifiable concentration data point for JTX-2011, nivolumab, pembrolizumab, or ipilimumab. Subjects in the PK analysis set with insufficient concentration data to calculate PK parameters will be included in the concentration data listings and summaries but excluded from the PK parameter listings and summaries.

## 6.3 TREATMENT MISALLOCATIONS

If subjects received the incorrect treatment(s) during the study, then the subjects will be reported under their planned treatment group for all efficacy analysis, but sensitivity analysis will be performed without these patients. For safety analysis, this subject will be reported under planned treatment group if less than half of the treatments were incorrect, otherwise will be reported under the actual treatment level.

# 7. GENERAL CONSIDERATIONS AND DATA HANDLING CONVENTIONS

## 7.1 FORMAT AND DISPLAY

All statistical analyses discussed in this SAP will be generated for the final CSR. All datasets, documentation, and the SAP will be archived in the Trial Master File (TMF). Tables, figures, and listings (TFLs), as described in this document and in the mock shells, will be created using SAS version 9.4 or higher. Mock table, listing, and figure shells will be developed for detailed presentation purposes. The mock tables, listings, and figure shells will not be considered as part of the SAP signoff.

TFL layout will be landscape. Margins will be a minimum as such: top 3/8 inch, bottom 3/8 inch, right 3/8 inch, and left 3/4 inch. Font will be a non-proportional courier new 8 or 9 pt font. Headers will include program name, associated project, and raw EDC data cut. Titles will generally have lines for Table/Figure/Appendix (i.e., Listing) with a number. Titles will include TFL numbers, where tables start with 14, listings with 16,

and figures with 14. Additional lines will include an appropriate title and study population for the output. All footnotes will be ordered by abbreviations, notes, and superscripted footnotes [1], [2], [3], etc. Report creation date and significant program modifications and date are documented in the SAS programs. At the bottom of each page a reference to the source data and the path of the program that created the TFL will be displayed. In some database systems, it is useful to extract a subset of data for use in the production of tables. The date of extraction printed will be the latest date upon which the extraction of contributing data occurred; which in some cases can come from multiple datasets.

"Source data" refers to the data listings of SDTM or ADaM data appropriate for the TFL.

Database lock will be performed when all EDC and external data have been cleaned. The final database lock date will be considered the date of the final extraction dataset date (EDC or external).

## 7.2 STANDARD SUMMARY STATISTICS

Summary will be provided separately for each Phase 1 part (A, B, E, G) by dose level and for each Phase 2 part (C, D) by tumor type cohort unless specified otherwise. A total column will also be provided in summary tables as appropriate. Descriptive statistics (n, mean, standard deviation, median, minimum and maximum) will be calculated for all continuous variables. Geometric mean, geometric coefficient of variation (GCV%), interquartile range (IQR:Q1-Q3) and 2 sided confidence intervals may also be presented as appropriate. For continuous parameters, the sample number will be displayed as a whole number. In general means and medians will be reported to one additional decimal place as compared to original data as collected and standard deviation will be reported to 2 additional decimal places. Minimums and maximums will be reported as collected. Data will be aligned by decimal place where appropriate. Column headers will have (N=) where applicable.

Frequencies and percentages will be presented for categorical and ordinal variables. Frequencies are not displayed for counts of zero. All frequency counts greater than 0 will have percentages displayed. Count and percentages will be displayed in the form xxx (xxx.x). All percentage columns will be right justified. Column headers will have (N=) and where applicable n (%).

## 7.3 BASELINE VALUE AND CHANGE FROM BASELINE

Unless otherwise specified, baseline values are defined as the most recent non-missing value obtained immediately prior to administration of first dose of study treatment and within 28 days prior to first dose. Change from baseline will be calculated by subtracting the baseline value from the post-dose assessment for each subject (i.e. post-dose minus baseline).

## 7.4 STUDY DAY

The first day of treatment will be designated as Study Day 1, which is also Cycle 1 Day 1 (C1D1). The day prior to the first day of treatment is Study Day-1, two days prior is Study Day -2, etc. Baseline or pre-treatment day/week/month/year calculations will be performed as date from first dose date minus closest date to first dose date, whereas post-baseline day/week/month/year calculations will be date from first dose date minus closest date to first dose date plus 1.

## 7.5 STANDARD DATE/DAY CONVERSION AND MISSING DATE CONSIDERATIONS

Dates will be formatted as YYYY-MM-DD (ISO-8601 Standard). For the purpose of converting days to years or months, one year = 365.25 days and one month = 30.4375 days.

### 7.5.1 MISSING DATES AND STUDY DAY DERIVATION

Dates missing the day, month, or year will be formatted to the following:

- If the eCRF has date fields for day, month, and year
  - Full date format:            YYYY-MM-DD
  - Missing day:                YYYY-MM
  - Missing day & month:    YYYY
- If the eCRF has date fields for month and year
  - Full date format:            YYYY-MM
  - Missing month:            YYYY
- If the eCRF has date fields for year
  - Full date format:            YYYY

Missing day, month, and year should be displayed with a dash “-“ for each character value missing so that it is known to be missing rather than a potential programming error. If options of “UNK=Unknown”, “ND=Not Done”, “NA=Not Applicable”, or “NS=Not Specified or No Sample” are indicated on the eCRF the acronyms should be included for their respective missing information. For the purposes of a listing, dates should reflect only the information provided by the investigator.

The study day derivation for missing or partially missing dates for purposes of calculations will be as follows:

- Missing start date (day) only: Impute with 01, unless data collected in other domains provide a reasonable timeframe of which the day can be inferred. Basis of day selection should be properly described in the program.

- Missing start date (month and day) only: Impute month as 01 and day as 01, unless data collected in other domains provide a reasonable timeframe of which the day can be inferred. Basis of day selection should be properly described in the program.
- Missing stop date (day) only: Impute with 30 or 31 (end of the month), unless data collected in other domains provide a reasonable timeframe of which the day can be inferred. Basis of day selection should be properly described in the program.
- Missing stop date (month and day) only: Impute month as 01 and day as 31, unless data collected in other domains provide a reasonable timeframe of which the day can be inferred. Basis of day selection should be properly described in the program.

For adverse events, if the subject died and AE stop date is missing, the date of death is assigned. Missing stop dates for ongoing adverse events are assigned to whatever is the maximum date between treatment discontinuation date, study discontinuation date, visit date, or onset date. If the subject does not record a date of discontinuation, the stop date is the maximum of onset date or visit date.

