9.4.8.1. Adverse Events

Adverse events will be classified into standardized terminology from the verbatim description (Investigator term) according to the most recent version of the MedDRA adverse event coding dictionary at time of data analysis. Adverse events will be presented by Preferred Term nested within System Organ Class (SOC). Verbatim description and Preferred Term and SOC MedDRA-level terms for all AEs will be contained in the data listings of the Clinical Study Report for this protocol.

Adverse events will be summarized by the incidence of AEs/SAEs by body system and by preferred term. The incidence of AEs/SAEs will be based on the numbers and percentages of subjects with AEs/SAEs. Although a MedDRA term may be reported more than once for a patient, that patient will be counted only once in the incidence count for that MedDRA term. The severity of the AEs/SAEs and the relationship to the study drug will be summarized for each body system and preferred term by treatment group. Withdrawals due to AEs/SAEs will be summarized for each body system and preferred term.

AEs/SAEs will be classified based on the AE start date in relation to the first dose date as the following:

- Treatment-emergent AEs, defined as AEs that newly emerge, re-emerge or worsen on or after the first dose of study drug; all these AEs would have a start date on or after the first dose date of the study drug.
- Pre-treatment events, defined as AEs that newly emerge, re-emerge or worsen before the first dose of study drug; all these AEs would have a start date before the first dose date of the study drug.
- Post-treatment events, defined as AEs that newly emerge, re-emerge or worsen after the treatment emergent period (defined in SAP) of the study drug; all these AEs would have a start date after the last day of the safety window of the study drug.

Only treatment emergent AEs will be summarized. All adverse events will be included in all AE data listings with flags indicating treatment emergent, pre- or post-treatment.

In consideration of the varying durations of treatments, the incidence of treatment emergent adverse event will be presented in the following ways, as appropriate, (1) by cohort and overall; (2) by time interval, depending on the distribution of duration of treatment, e.g., by 1-, 3-, 6-, or 12-month intervals from start of therapy; and (3) by event rate per patient year (i.e., # of events per patient per year).

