## **8. ENDPOINT DEFINITIONS AND DERIVATIONS**

### **8.1 SAFETY DEFINITIONS AND ENDPOINTS**

#### **8.1.1 ADVERSE EVENT ENDPOINTS**

Adverse events will be categorized by pre-existing, treatment emergent and post treatment.

- Pre-existing AEs are designated to events that occur prior to the first dose of study drug(s) or observed prior to first dose but did not increase in NCI CTCAE toxicity grade during treatment period.
- Post-treatment adverse events will be any adverse events reported outside the 28 day post dose treatment window until the end of study participation. Any subsequent non-protocol treatment for the cancer diagnosis will end the potential study drug(s) adverse event data collection.
- Treatment-Emergent Adverse Events (TEAEs) are designated to events that occur after the start of study drug(s) and on or before 28 days after final dose of study drug, and were not observed prior to start of treatment; Or if the event was observed prior to the start of study drug but increased in NCI CTCAE grade after either the start of study drug or prior to 28 days after the final dose of study drug. Pre-existing adverse events may be reclassified as TEAEs if the frequency of the event increases during treatment.
- Treatment Related TEAEs will include those TEAEs which are possibly or probably related to study drug(s) as designated by the investigator. Events having a missing relatedness will be designated as definitely related on tables but the listing will display the data as collected. Relationship may be attributed by JTX-2011 and/or nivolumab/ipilimumab/pembrolizumab and will be displayed separately.
- Serious adverse events (SAEs) will include all events classified as serious on the eCRF. The electronic database used to enter data at the site (i.e., RAVE / iMedidata) will be deemed as the complete report for adverse event information. The pharmacovigilance database will be reconciled against the EDC.

- Infusion related reactions (IRRs) may be captured as an adverse event as well as the symptoms that cause the IRR. Symptoms of IRRs are events occurring shortly after or during the study drug infusion. Symptoms may include but are not limited to: flushing, headache, nausea, fever, chills, dyspnea, rash, hypotension, wheezing, coughing, tachycardia. Any sign/symptom determined to be associated with an IRR may be counted as such in adverse event reporting. The highest grade sign/symptom must be associated with the IRR preferred term.

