### 9.9.1 ADVERSE EVENTS

Adverse events (AEs) will be listed and summarized using MedDRA v19 coded terms. Listings will be created by categories for AEs as outlined below:

- All adverse events (AEs) with flags for treatment emergent adverse events (TEAEs) and flags of relatedness to study drug(s)
- SAEs with flags for treatment emergent adverse events (TEAEs) and flags of relatedness to study drug(s)
- Immune related adverse events (irAEs)
- Infusion related reactions (IRRs)
- TEAEs leading to death
- TEAEs leading to study drug interruption, reduction, hold or permanent study drug discontinuation
- TEAEs considered as DLTs

A general overview summary table will include frequencies by category of AE (as listed above) and will also include TEAE by severity grade and relationship to study drug (both JTX-2011 and/or nivolumab and/or ipilimumab and/or pembrolizumab).

Frequencies and percentages will be reported by System Organ Class (SOC) and Preferred Term (PT). Patients with multiple events for a category will be counted once in the highest CTCAE classification. Summary tables will include treatment-emergent AEs, unless specified otherwise. Missing onset date for an event will be considered as TEAE. If relatedness is missing the adverse event will be considered related. The denominator (N) for adverse events reported at each cycle will include SAF patients who are dosed at least once in that cycle. Important note: Patients will be counted in terms of number and adverse event in the actual dose group as received, not the as intended dose group. Summary tables by SOC and PT will be sorted in descending frequency of SOC for the total column, then in descending frequency of PT within SOC for the total column. Summary tables by PT will be sorted in descending frequency of PT for the total column.

The following summary TEAE tables listed in Table 7 below will be presented for Phase 1 and Phase 2 parts. In addition, DLTs will be summarized by SOC and PT only for Phase 1 parts (A, B, E, G) for DLT Evaluable Set.

Table 7 Summary of Adverse Event Displays

Category	TEAE	IRR	irAE	TEAE Related to JTX2011	TEAE Related to Any Study Drug	Serious TEAE	Related SAE	TEAE Resulting in Death	TEAE Resulting in Dose Interruption, Reduction or Hold	TEAE Resulting in Study Drug Discontinuation
SOC and PT	X			X	X	X	X			
SOC/PT/Max. Grade	X			X	X					
SOC/PT/Max. Grade $\geq 3$				X						
SOC/PT by Cycle	X									
SOC/PT by Grade, Cycle										

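### By default a partial adverse event onset date is imputed to the 1st with no floor at first dose, and this is not reconciled with the rule that counts a missing onset as treatment-emergent

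*SAP*

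**What the plan says.** SAP section 7.5.1 introduces its rules with "The study day derivation for missing or partially missing dates for purposes of calculations will be as follows". They are general and not specific to adverse events. For start dates they are "Missing start date (day) only: Impute with 01" and "Missing start date (month and day) only: Impute month as 01 and day as 01". Both carry the same exception: the default holds "unless data collected in other domains provide a reasonable timeframe of which the day can be inferred", with the basis for the choice described in the program. The section's paragraph on adverse events deals only with stop dates.

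SAP section 8.1.1 defines treatment-emergent events as "events that occur after the start of study drug(s) and on or before 28 days after final dose of study drug", or events already present that rise in grade. Events before first dose are pre-existing. Protocol section 9.4.8.1 also classifies by start date: for treatment-emergent events, "all these AEs would have a start date on or after the first dose date of the study drug". Summary tables normally show treatment-emergent events only.

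SAP section 9.9.1 adds a default for adverse events: "Missing onset date for an event will be considered as TEAE". It does not mention partly missing dates and does not refer back to 7.5.1.

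**The concern.** An onset recorded only as March 2018, in a subject first dosed on 15 March 2018, becomes 1 March under the default. The event is then pre-existing and leaves the summary tables. If the site had recorded no onset date at all, 9.9.1 would have counted it. Knowing more about the date therefore makes the handling less conservative. That is out of line with the rest of 9.9.1, where missing relatedness is taken as related.

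Safety and tolerability are primary objectives in both phases (SAP section 3.2.1). The treatment-emergent tables are exposed, including those by cycle, as are any infusion-reaction and immune-related tables built on the same classification. Adverse events are collected from consent (Protocol section 8.14.2), so a pre-dose category exists and a misplaced event in it would not look odd.

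**Working it through.** The documents give no figure on this point, so there is none to reproduce. The check applies the 7.5.1 default to the calendar.

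**Inputs from the documents:** day set to 01, or month and day set to 1 January (SAP 7.5.1); classification by onset relative to first dose (SAP 8.1.1, Protocol 9.4.8.1); Cycle 1 of 21 or 42 days (the q3w and q6w schedules).

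**Assumptions not in the documents:** first-dose dates are uniform over a four-year calendar (1,461 days); onsets are uniform over Cycle 1; the exception is not used; the 9.9.1 default is not applied to partial dates.

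**Step 1: share of first-dose dates for which the imputed date falls before dosing.** Four years contain 48 firsts of the month and 4 first Januaries.
- Day missing: (1461 − 48)/1461 = 96.7%.
- Month and day missing: (1461 − 4)/1461 = 99.7%.

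These apply to onsets in the month (or year) of first dose. They are not shares of Cycle 1 events.

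**Step 2: share of Cycle 1 onset days moved to before dosing.** For first dose on day d of an m-day month and a cycle of L days, the affected onset days number min(L, m − d + 1) if d > 1, and 0 if d = 1. Dividing the sum over d by m × L gives, for m = 30:
- L = 21: (9 × 21 + (20 + 19 + … + 1))/(30 × 21) = (189 + 210)/630 = 63.3%.
- L = 42: (29 + 28 + … + 1)/(30 × 42) = 435/1260 = 34.5%.

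Enumerating the actual calendar, with its unequal months, gives:

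| Missing part | 21-day Cycle 1 | 42-day Cycle 1 |
|---|---|---|
| Day | 63.9% | 35.1% |
| Month and day | 97.0% | 94.1% |

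**Step 3: two cases.** First dose is 15 March 2018 in both. A true onset of 20 March with the day missing becomes 1 March, before dosing. A true onset of 2 April with the day missing becomes 1 April, still after dosing. The problem is confined to the month (or year) of first dose.

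**Step 4: the other reading.** If the 9.9.1 default covers partial dates, or if the first dose date is used as other-domain data to place the onset, the number moved is 0.

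**Step 5: scale of one event.** One lost event changes incidence by 1/15 = 6.7 points in a cohort of 15, and by 1/6 = 17 to 1/3 = 33 points in a dose cohort of 6 or 3. This holds only if that subject has no other event under the same term, because subjects are counted once per term.

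**The case against.** A reader might infer that the plan drops these events outright. The text does not go that far. Section 7.5.1 labels a day-missing date as a kind of missing start date, so the rule in 9.9.1, being specific to adverse events, can be read as covering it. The exception also gives the programmer a way out. Early visits are dense in Phase 1 (Days 1, 2, 8 and 15 of Cycle 1, plus Day 4 for sentinel subjects), so other data may often place the onset. Onset dates must be recorded, missing data are queried and lock follows cleaning, so partial dates may be few. Listings include all adverse events and show dates as reported. Some partial dates in the first-dose month will truly precede dosing, since screening can start 28 days earlier.

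These points limit the claim but do not remove it. Protocol section 9.4.6, on medications, expressly covers partly missing dates; SAP 9.9.1 does not. If 9.9.1 were meant to override the imputation, the SAP should say so. The exception does not name first dose as a floor, and a first dose date alone does not identify an onset day. The choice is left to program documentation in an open-label study. The grade-increase route in 8.1.1 rarely helps: a new event with a single record has no earlier grade to exceed.

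A reader might also infer an undercount of dose-limiting toxicities. The documents do not support that. These are determined by toxicity in Cycle 1 and reviewed by the Safety Monitoring Committee, not derived from an imputed date. SAP section 4 describes the Phase 1 parts as completed, so this SAP, dated March 2020, could not have influenced escalation.

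**Conclusion.** The point holds as a default that gives the wrong result for partial onset dates in the month or year of first dose, together with two SAP sections that are not reconciled. The treatment-emergent count depends on which section is followed. The number of events lost ranges from none to every day-missing onset in the first-dose month, apart from subjects dosed on the 1st and events that qualify through a grade increase. The month-and-day-missing rule has the same gap over a whole year.

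The shares of 63.9% and 35.1% are conditional on the day being missing and the default being applied, with uniform dates. The 96.7% describes first-dose dates, and reading it as the share of Cycle 1 events lost would overstate the problem. The documents do not say how many onset dates are partial, so a real undercount is possible but not demonstrated.

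**What to change.** Add to SAP section 9.9.1, stated to override 7.5.1 for adverse events:

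- An event with a partial onset date counts as treatment-emergent unless the known parts of that date, or the stop date, show onset before first dose. The 28-day end of the window in 8.1.1 is unchanged.
- If the known month and year (or year alone) match those of first dose, impute the first dose date. Otherwise use day 01 (and month 01).

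The stop date should be used as reported, not as imputed: 7.5.1 sets a stop date with month and day missing to 31 January, which could itself wrongly place the event before dosing.

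In the calendar enumeration for day-missing onsets, the imputation step leaves 0 on-treatment onsets before first dose. For year-only onsets the result is also 0 by construction, since the imputed date is either the first dose date or 1 January of a later year.

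The cost is a short addition to the SAP and a small programming change. A few events that truly began before dosing may be counted as treatment-emergent, which is the conservative direction for safety reporting.

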9.4.6. Concomitant Medication

Medications used in this study will be coded by using the World Health Organization Drug Dictionary Enhanced (WHO-DDE) and categorized as the following:

- **Prior medication:** any medication that started before the first dose of study drug, regardless of when the medication ended.
- **Concomitant medication:** medication continued or newly received at or after the first dose of study drug through the end of treatment emergent period (defined in the SAP).
- **Post-treatment medication:** medication continued or newly received after the treatment emergent period.

A given medication can be classified as a prior, a concomitant, or a post-treatment medication; both prior and concomitant; both concomitant and post-treatment; or prior, concomitant, and post-treatment. If a medication has a missing or partially missing start/end date and it cannot be determined whether it was taken before the first dose, concomitantly, or beyond the treatment emergent period, it will be considered as prior, concomitant, and post-treatment.

For the SAF, prior medications and concomitant medications will be summarized descriptively by: 1) preferred name; and 2) anatomic class (ATC) level 1, ATC level 2, and preferred name. Post-treatment medications will be listed by subject.

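### SAP 7.5.1 sets a year-only stop date to 31 January, very likely a slip for 31 December; this can put a stop before its start or before first dose

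*SAP*

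**What the plan says.** SAP 7.5.1 sets default dates for use in calculations. Four of its rules matter here.

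- Start known only to the year: "Missing start date (month and day) only: Impute month as 01 and day as 01". This is the earliest possible date.
- Stop missing only its day: "Missing stop date (day) only: Impute with 30 or 31 (end of the month". This is the latest possible date.
- Stop known only to the year: "Missing stop date (month and day) only: Impute month as 01 and day as 31". This is 31 January.
- Adverse events have their own rule: "Missing stop dates for ongoing adverse events are assigned to whatever is the maximum date between treatment discontinuation date" and several other dates, including onset. If the subject died, the date of death is used.

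The first three are defaults, which hold "unless data collected in other domains provide a reasonable timeframe of which the day can be inferred". The section sets no floor at the record's own start date. Listings are to show only what the investigator reported.

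Protocol 9.4.6 defines a prior medication as "any medication that started before the first dose of study drug, regardless of when the medication ended" and a concomitant one as "medication continued or newly received at or after the first dose of study drug through the end of treatment emergent period". If a partial date leaves the timing undetermined, "it will be considered as prior, concomitant, and post-treatment". SAP 9.6 (Concomitant Medication) neither repeats nor replaces that rule, and the SAP does not say whether the 7.5.1 imputation or the protocol rule is applied first.

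**The concern.** The rules next to it follow one logic: starts go as early as possible and stops as late as possible, so that no exposure is lost. The year-only stop rule breaks it. Day 31 combined with month 01 is close to the earliest date in the year, and reads like month 12 mistyped.

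Three things are at stake. A derived stop can precede its own start or the first dose. A drug that was still being taken after first dose can be classed as prior only, against the inclusive rule in Protocol 9.4.6. And SAP 9.2 summarises time since last anti-cancer treatment; if the same rule is used for prior-therapy stop dates, that interval is lengthened.

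**Working it through.** The plan gives no figure to reproduce, so the check is a count of calendar days. **Assumption, not in the documents:** the start date (or first dose) is spread evenly over a 365-day year.

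**1. Stop year equal to the start or first-dose year.** The imputed stop is day 31 of the year. It precedes any start or first dose on days 32 to 365: 365 − 31 = 334 days, and 334/365 = 91.5% (335/366 = 91.5% in a leap year).

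**2. By true interval D, in days, from start (or first dose) to stop.** With the start on day s, the imputed stop precedes it only if s is at least 32 and the true stop, s + D, is still in the same year. The number of such days is 365 − D − 31 = 334 − D, so the share is (334 − D)/365, and zero from D = 334.

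| D (days) | Calculation | Imputed stop before start or first dose |
|---|---|---|
| 7 | 327/365 | 89.6% |
| 30 | 304/365 | 83.3% |
| 90 | 244/365 | 66.8% |
| 151 | 183/365 | 50.1% |
| 152 | 182/365 | 49.9% |
| 180 | 154/365 | 42.2% |
| 270 | 64/365 | 17.5% |
| 334 or more | 0/365 | 0% |

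The 50% point is at about 151 days, or 151/30.4375 = 5.0 months. If the stop year is later than the start or first-dose year, the problem cannot arise. With 31 December of the known year, the share is 0% in every row.

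**3. Illustration.** Take an assumed first dose on 15 June 2018 and a stop recorded as 2018. Under SAP 7.4, 31 January is Study Day −135 and 31 December is Study Day 200.

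**4. Who can lose concomitant status.** Under Protocol 9.4.6, a drug with a known start on or after first dose is concomitant by its start date, whatever the stop. Two routes remain, both needing a stop in the first-dose year and a first dose after 31 January:

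- a drug started before first dose, with a year-only stop;
- a drug with both dates year-only, which SAP 7.5.1 turns into 1 to 31 January.

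In both, Protocol 9.4.6 would count the drug in all three classes. It becomes prior-only only if the SAP imputation is applied first and its result is treated as a known date.

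**5. Prior therapy.** If the true stop is spread evenly over the known year, its mean is day 183. The imputed date is then 183 − 31 = 152 days too early on average (152/30.4375 = 5.0 months), and at most 365 − 31 = 334 days (334/30.4375 = 11.0 months). Time since last treatment is overstated by that amount. This applies to stop years before the first-dose year; in the first-dose year, the first dose itself limits the true date.

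**The case against.** The strongest defence is that the rule is only a default and that other text contains the damage. Data from other domains can override it, and Protocol 3.8.1 has concomitant medication documented at every visit, so on-study drugs may often have bounding information. Protocol 9.4.6 covers exactly the medications whose timing is unclear. Adverse events have separate stop-date rules. These points stand and narrow the concern. They do not remove it: a record's own start date is not in another domain, a first-dose date does not show when a drug ended, and nothing in the SAP puts the protocol rule first.

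Four stronger readings are tempting and are not supported:

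- *Steroids given for immune events on study would vanish from the concomitant summary.* With a known start after first dose they stay concomitant. Only a record with both dates year-only is exposed.
- *Ongoing drugs would become prior-only.* The rule needs a known stop year; a drug that is still ongoing has none. The exposed drugs are those that continued past first dose and then stopped.
- *About 92% of year-only records would be misclassified.* The 91.5% is the share of date reversals when the years coincide. It is not a misclassification rate, and it falls with the interval as shown above.
- *Negative durations would reach the tables.* SAP 9.6 plans counts by drug class and term, without duration. SAP 9.9.1 plans incidence tables. A treatment-emergent event (SAP 8.1.1) is defined by when it occurs. Treatment duration (SAP 9.7 and 9.8.1) uses dosing and end-of-treatment dates.

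**Conclusion.** The concern holds in limited form. SAP 7.5.1 states a derivation rule that is inconsistent with its own neighbouring rules and very likely contains a slip. When the stop year equals the start or first-dose year, and dates are evenly spread, it reverses the order of dates in about 91.5% of cases. The share is about 50% at a true interval of about five months, and nil at 334 days or more or with a later stop year.

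Loss of concomitant status is conditional on the SAP rule being applied ahead of Protocol 9.4.6. The lengthening of time since last anti-cancer treatment, about 5 months on average per affected record, is conditional on the rule being used for prior therapy.

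The documents do not say how many stop dates are known only to the year, so the overall effect cannot be sized. No primary endpoint is shown to be affected: response, progression-free survival and overall survival (SAP 8.3) rest on scan, death and first-dose dates. It is worth correcting because the rule as written gives wrong dates and the correction is cheap.

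**What to change.** In SAP 7.5.1, impute a year-only stop date to 31 December of that year, never before the record's start date, and capped at the earliest of death, last contact and data cut-off. For prior anti-cancer therapy, also cap it at the day before first dose. Without that cap, a stop in the first-dose year could fall after first dose, contradict the washout periods in Protocol 4.2, and make the time since last treatment negative.

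In SAP 9.6, state that Protocol 9.4.6 governs medication classification when dates are partial.

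The change does not make the prior-therapy interval exact. Before any cap, 31 December is on average 365 − 183 = 182 days later than an evenly spread true date, so that interval would then be understated. A footnote giving the number of imputed dates in that summary would let the reader judge.

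The cost is a line or two in each of two SAP sections, an edit to the date-imputation program, and the additional signatures that SAP section 2 requires for an update after approval. No new data are needed.
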